### 9.2 DESCRIPTION OF STATISTICAL METHODS

#### 9.2.1 GENERAL APPROACH

This is a pilot study to assess the feasibility of bridge-to-transplantation using SBRT for patients with severe liver disease.

#### 9.2.2 ANALYSIS OF PRIMARY ENDPOINT

Using the efficacy analysis set, the proportion of transplant eligible participants at 1 year (per Milan criteria, Section 7.5) will be measured from time of first SBRT dose, reported with 95% exact confidence interval (CI).

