## SYNOPSIS

Study Title	A pilot study to assess feasibility of stereotactic body radiation therapy for hepatocellular carcinoma patients awaiting liver transplantation
Protocol #	18810
Study Center	OHSU, single-site
Clinical Phase	Pilot
Investigational Component(s)	Radiation Therapy
Interventional Study Type	Single-arm
Précis	
Liver transplantation (LTx) is the best treatment for patients with hepatocellular carcinoma (HCC) and Child-Pugh (CP) B or C cirrhosis, as both conditions can be very effectively treated at once. As liver transplantation wait-lists can be many months, liver directed therapies (LDTs) are essential as oncologic temporizing measures to bridge patients to transplantation. However, due to the fear of further hepatic decompensation, many patients with advanced cirrhosis are excluded from receiving LDTs. This study hypothesizes that liver stereotactic body radiation therapy (SBRT) can be of safe and practical use in this fragile patient population and may result in the reduction of transplantation drop-out rates. The overall goal of this pilot proposal is to evaluate the feasibility of bridge-to-transplantation liver SBRT in hepatocellular carcinoma patients with Child-Pugh B8 or higher cirrhosis.

Primary Objectives	Assess the use of SBRT in HCC patients with advanced liver cirrhosis as a feasible approach to providing localized disease control that adequately suffices liver transplant eligibility criteria.
Secondary Objectives	Assess preliminary efficacy and toxicity in HCC patients with advanced cirrhosis following liver SBRT
Exploratory Objectives	
Assess quality of life (QoL) in HCC patients with advanced cirrhosis following liver SBRT
 
Examine SBRT-related histopathologic changes in explanted livers of patients with advanced cirrhosis.

Primary Endpoints	
 
1. Proportion of participants that are transplant eligible 1 year following SBRT
 

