### 3. STUDY DESIGN AND ENDPOINTS

#### 3.1 DESCRIPTION OF THE STUDY DESIGN

*Refer to Section 9, Statistical Considerations, for additional information regarding statistical methods used in this study.*

This is pilot study to assess the feasibility of bridge-to-transplantation SBRT for patients with severe liver disease. Participants must meet the inclusion criteria, have none of the exclusion criteria, and have provided written informed consent before the conduct of any screening tests not performed routinely in their treatment.

In general, patients with CP-B8 or higher cirrhosis and non-metastatic HCC who have been listed or recommended to be listed for liver transplantation will be eligible for participation in this study. Eligible participants will undergo SBRT consisting of 40 Gy to be given in 5 fractions every other day provided that criteria for normal organ constraints are met (i.e.,  $\geq 700$  cc of uninvolved liver). In cases where normal organ constraints are not met, the dose will be iteratively de-escalated to two dose levels (35 Gy in 5 fractions, then 30 Gy in 5 fractions). If normal organ constraints are unable to be met at 30 Gy in 5 fractions, the participant will be considered ineligible for SBRT and considered a screen failure.

Following SBRT, the rate of radiation-induced liver disease (non-classical RILD) and associated toxicities will be evaluated, along with treatment response and an assessment of quality of life associated with SBRT. The proportion of participants that are successfully bridged to liver transplantation, and times to liver transplantation following SBRT will be recorded for each participant. Additional exploratory studies will assess SBRT-related histopathologic changes in explanted livers of participants with advanced cirrhosis. In these studies, pathologic treatment response in explanted livers will be evaluated, and regions of uninvolved liver both near and remote to the irradiated volume will be assessed for histopathologic changes consistent with RILD (e.g., obliteration of central veins, increased perisinusoidal reticulin network and hepatocyte necrosis).

This study aims to enroll 15 participants at OHSU. Participant data for primary, secondary, and exploratory endpoints will be collected by the site providing clinical care. The analyses of the data collected will take place at OHSU.

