#### 3.2 STUDY ENDPOINTS

##### 3.2.1 PRIMARY ENDPOINT

Endpoint	Start	End
Proportion of participants who are transplanted or with localized disease control that meets Milan criteria (Section 7.5) within 1 year	Start of SBRT	Time of progression, or transplantation, or 1-years after last SBRT dose, whichever occurs first

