## 7.3 EFFICACY CRITERIA FOR TUMOR RESPONSE

### 7.3.1 EVALUATION OF TARGET LESION

**Progressive Disease (PD):** An increase of at least 20% in the sum of the diameters of viable (enhancing) target lesions, taking as reference the smallest sum of the diameters of viable (enhancing) target lesions recorded since treatment started

**Non-Progressive Disease** Any cases that do not qualify for progressive disease

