### 7.3.3 LOCAL CONTROL RATE

Local control is defined as the absence of progressive disease (per Section 7.3.1) within the PTV or at the PTV margin, measured from time of first SBRT dose to time of progression or transplantation, or 2 years from last SBRT dose, whichever occurs first.

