## 9. STATISTICAL CONSIDERATIONS

Refer to Section 3.1, *Description of the Study Design* for a detailed description of the study design and endpoints.

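### The single primary endpoint has two definitions: Section 3.2.1 counts transplantation within a year as success, while Section 9.2.2 and the synopsis count only transplant eligibility at one year

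*Combined protocol and SAP*

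**What the plan says.** The primary endpoint is stated in three places.

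- Section 3.2.1 (endpoint table): "Proportion of participants who are transplanted or with localized disease control that meets Milan criteria (Section 7.5) within 1 year". The window opens at the start of SBRT and closes at "Time of progression, or transplantation, or 1-years after last SBRT dose, whichever occurs first".
- Section 9.2.2 (analysis): "the proportion of transplant eligible participants at 1 year (per Milan criteria, Section 7.5) will be measured from time of first SBRT dose", in the efficacy analysis set, with an exact 95% interval.
- Synopsis (endpoint line): "Proportion of participants that are transplant eligible 1 year following SBRT".

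Section 7.5 defines eligibility by tumor number and size and by absence of major-vessel or extrahepatic involvement. It does not address a participant who has already been transplanted. The primary objective, in the synopsis and Section 2.1, does name localized disease control, but it does not make transplantation a primary success.

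Section 9 refers the reader to Section 3.1 "for a detailed description of the study design and endpoints". Section 3.1 does not state the primary endpoint. On transplantation it says: "The proportion of participants that are successfully bridged to liver transplantation, and times to liver transplantation following SBRT will be recorded". Section 9.2.3 analyses the proportion transplanted as a separate secondary endpoint, whose window in Section 3.2.2 runs to two years.

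**The concern.** A participant transplanted at, say, month 5 is a success under Section 3.2.1. Under Section 9.2.2 the same participant has no tumor-bearing liver to assess against Section 7.5 at one year, and could be scored as eligible, scored as not eligible, or left out. The text supports no one of these over the others. Reporting transplantation separately as a secondary endpoint makes it easier to read Section 9.2.2 as excluding it from the primary.

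The time frames differ as well. Section 3.2.1 says within a year and closes one year after the last dose. Section 9.2.2 says at one year and counts from the first dose. The synopsis says one year following SBRT.

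Section 1.3 says the pilot is meant to help estimate bridging efficacy against historical controls for a larger trial, so the primary proportion and its interval are a main product of the study. In an open single-arm trial, a definition settled after the outcomes are known is an avoidable source of bias.

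**Working it through.** **The plan's own figure.** Section 9.3.1 justifies N = 15 by the chance of meeting at least one SBRT-ineligible patient when the probability is 20%. The required n is ln(0.05)/ln(0.80) = 13.4, rounded up to 14. At n = 15 the chance is 1 − 0.80^15 = 96.5%. The stated 15 is therefore adequate for that purpose, and it does not depend on how the primary endpoint is defined.

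**Inputs for the illustration.** These are assumptions sized from the protocol's background figures, not forecasts.

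- 15 evaluable participants.
- Transplanted before one year: 4. Section 1.2.1 reports 13 of 51 patients with CP-B8 or worse; 13/51 = 25.5%, and 0.255 × 15 = 3.8. That series gives no time limit and mixes SBRT with another hypofractionated schedule.
- Beyond Milan: 4. Section 1.1 gives 20–30% of listed patients over the waiting period; × 15 = 3.0 to 4.5.
- Controlled and inside Milan at one year: 15 − 4 − 4 = 7.

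**Calculation.** Hold 4 participants beyond Milan and let T be the number transplanted, so that 11 − T are controlled inside Milan. Section 3.2.1 then gives 11/15 = 73% (Clopper-Pearson 95% CI 45–92) for every T. Section 9.2.2 gives (11 − T)/15 if transplanted participants score as not eligible, and (11 − T)/(15 − T) if they are excluded.

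| T | Section 9.2.2, scored not eligible | Gap from 73.3% | Section 9.2.2, excluded | Gap from 73.3% |
|---|---|---|---|---|
| 2 | 9/15 = 60% (32–84) | 13.3 points | 9/13 = 69% (39–91) | 4.1 points |
| 4 | 7/15 = 47% (21–73) | 26.7 points | 7/11 = 64% (31–89) | 9.7 points |
| 6 | 5/15 = 33% (12–62) | 40.0 points | 5/9 = 56% (21–86) | 17.8 points |

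With T = 4 and 3 or 5 beyond Milan, Section 3.2.1 gives 12/15 = 80% or 10/15 = 67%. Scoring transplanted participants as not eligible gives 8/15 = 53% or 6/15 = 40%. The gap stays at 4/15 = 26.7 points.

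**Local control.** Section 7.3.3 says: "Local control is defined as the absence of progressive disease (per Section 7.3.1) within the PTV or at the PTV margin". Section 7.3.1 sets progression of target lesions at: "An increase of at least 20% in the sum of the diameters of viable (enhancing) target lesions". A lesion can grow that much and remain inside Milan. If Section 3.2.1 uses the Section 7.3.3 definition, such a participant fails there but is eligible under Section 9.2.2. The background figures give local failure of 3% (one-year control of 97% with SBRT in the retrospective series) to 7% (six-month control of 93% in CP-B), that is 0.03 × 15 = 0.45 to 0.07 × 15 = 1.05 participants. This is an upper bound, since not every local failure stays inside Milan. One participant is 1/15 = 6.7 points.

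**The case against.** The strongest defence is that the intent is plain. In a bridge-to-transplant study nobody would count a transplanted participant against the treatment, and Section 3.2.1 says outright that transplantation is a success. Times to transplantation are to be recorded for each participant (Section 3.1), so the composite can be computed whatever Section 9.2.2 says. There is no hypothesis test or threshold.

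Much of this stands. A reader might infer that the one-year composite could not be recovered because the transplant proportion is reported over two years; the recorded transplant times rule that out. What the defence does not supply is a statement that Section 3.2.1 governs. The analysis section, which the analyst will follow, omits transplantation, and the cross-reference in Section 9 leads to a section without the primary endpoint.

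Three other stronger readings are also unsupported.

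- That the error is 27 points, or up to 40. This takes only the harshest scoring of transplanted participants; exclusion is equally open and gives about 10 points, or up to 18.
- That participants with progression at the PTV but inside Milan are definitely scored differently in the two sections. Section 3.2.1 cites only Section 7.5, not Section 7.3.3, and with the objective in Section 2.1 can be read as disease contained enough to meet Milan.
- That deaths would be dropped from the denominator. Section 9.4 does not call for that. The end column of Section 3.2.1 omits death, which is a reason to state the scoring but not evidence of an intended exclusion.

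**Conclusion.** The point holds and should be fixed. The definitions of the only primary endpoint disagree on whether transplantation within a year is a success, and also on time origin and cut-off, and no passage reconciles them. With 4 beyond Milan and 2 to 6 of 15 transplanted, Section 9.2.2 read literally falls below Section 3.2.1 by 13 to 40 points if transplanted participants score as not eligible, or by about 4 to 18 points if they are excluded. These sizes rest on assumed counts, and the illustration includes no deaths before one year.

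The local-control ambiguity is secondary, at about 0 to 1 participant. The consequence is limited to the descriptive primary estimate and its interval; a reader should not infer that the sample size or any decision rule is undermined. Nor does the synopsis ignore local control altogether: its objective names it, while its endpoint line does not.

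**What to change.** 1. Use the Section 3.2.1 composite in the synopsis and Section 9.2.2. State that transplantation within one year counts as success and that death before transplant within one year is a non-success in the efficacy set.
2. Use one time origin and one one-year cut-off in the synopsis, Section 3.2.1 and Section 9.2.2.
3. State whether localized disease control in Section 3.2.1 means the Section 7.3.3 definition or only disease within Milan, and whether progression that stays inside Milan is a failure. These choices belong to the sponsor; report the other reading as a sensitivity analysis.
4. Reconcile the synopsis follow-up duration and Section 4.7, under which progression can end follow-up, with Section 6.5, under which follow-up continues, so that one-year status is collected after progression.

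The cost is a few wording changes. Sample size and the exact interval method are unchanged. The downsides are that the reported proportion may be lower than one that leaves deaths out, and that one-year status is needed for participants who progress earlier. Section 6.5 already provides for that follow-up.

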#### 9.2.3 ANALYSIS OF THE SECONDARY ENDPOINTS

Using the efficacy analysis set, the estimate of local control rate, intrahepatic progression free survival, and overall survival, will be plotted using Kaplan-Meier curve and reported with median survival and 95% CI if available. Using the same efficacy analysis set, the proportion of participants that proceed to transplantation, will be measured and reported with 95% CI.

Non-classic RILD, liver toxicity defined as a  $\geq 2$  increase in CP score (**Appendix A**), and liver toxicity per CTCAE v5.0, will be estimated along with an exact CI using the safety analysis set.

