Secondary Endpoints	
 
1. Incidence of progressive disease within or at the planned tumor volume (PTV) margin (i.e. local control)
 
2. Incidence of progressive disease within any section of the liver, including the PTV (e.g. intrahepatic disease free survival)
 
3. Incidence of progressive disease outside of the liver (e.g. extrahepatic disease free survival)
 
4. Overall Survival
 
5. Proportion of participants that proceed to transplantation
 
6. Incidence of non-classical radiation-induced liver disease (RILD), defined as grade 4 aspartate aminotransferase or alanine aminotransferase elevation, or an increase in CP score of <math>\geq 2</math> within 1 week to 3 months after completing SBRT.
 

	7. Incidence of liver toxicity per CTCAE v5.0 within 1 week to 3 months after completing SBRT.
Exploratory Endpoints	
 
1. QoL scores for EORTC QLQ-C30 questionnaire
 
2. QoL scores for Functional Assessment of Cancer Therapy-Hepatobiliary (FACT-Hep) questionnaire
 
3. At time of transplantation, histopathologic changes in irradiated tumor sites relative to uninvolved liver tissue will be assessed
 

Number of Participants	15
Duration of Therapy	SBRT will be administered as 5 fractions every other day (~10 day)
Duration of Follow Up	Time of progression, or transplantation, or 2-years after last SBRT dose, whichever occurs first
Key Inclusion Criteria	
 
1. Participants aged <math>\geq 18</math> years
 
2. Patient diagnosed with HCC and recommended for LTX
 
3. Meets clinical criteria for eligibility for SBRT to the target lesion
 
4. Childs-Pugh Class B8 or higher
 
5. Eastern Clinical Oncology Group performance status <math>\leq 2</math>
 
6. Safe radiation treatment planning parameters that adhere to all organs at risk constraints per section 5.1 of the protocol. If normal organs at risk constraints (including at least 700cc of uninvolved liver) are unable to be met at the lowest dose modification (30 Gy in 5 fractions), the patient is deemed ineligible for SBRT and deemed a screen failure.
 

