## 1.4 POTENTIAL RISKS AND BENEFITS

#### 1.4.1 KNOWN POTENTIAL RISKS

The use of SBRT is associated with increased risk for radiation-induced liver disease and further decompensation of liver function. At Oregon Health and Science University, the treatment of patient with severely compromised liver function is associated with a 31% increase in liver toxicity, as determined by an increase CP score of  $\geq 2$  within 6 months after SBRT. Only 11 of 146 patients (7.5%) were observed to have a Grade 4 toxicities (per Common Terminology Criteria for Adverse Event [CTCAE] criteria) within 6 months of RT. These grade 4 AEs consisted of 1 gall bladder perforation, 4 cases of thrombocytopenia, 2 cases of hyperbilirubinemia, 2 cases of upper gastrointestinal bleeding, and 2 cases of encephalopathy; however, no definitive treatment-related deaths were seen. In comparison, authors of a separate institutional study observed that 26% of 101 patients with baseline CP-A cirrhosis and 7 of 13 (53%) of patients with CP-B7 cirrhosis experienced CP  $\geq 2$  toxicity within 3 months of 6-fraction SBRT. However, it is very challenging to discern treatment-related hepatic toxicity from natural decline of hepatic functionality secondary to advanced cirrhosis. For example, the SHARP trial, a randomization of placebo versus sorafenib for advanced HCC, identified that the placebo arm had a 52% rate of adverse events likely due to cirrhosis or HCC progression. Refer to Section 8.4 for additional information.

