## 2.2 SECONDARY OBJECTIVES

Assess preliminary efficacy and toxicity in HCC patients with advanced cirrhosis following liver SBRT.

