##### 3.2.2 SECONDARY ENDPOINTS

Endpoint	Start	End
1. Localized control rate: Incidence of progressive disease within or at the planned tumor volume (PTV) margin		Time of progression, transplantation, death or 2-years after last SBRT dose, whichever occurs first.
2. Incidence of intrahepatic progressive disease		
3. Incidence of extrahepatic progressive disease		
4. Proportion of participants that proceed to transplantation	First dose of SBRT	
5. Overall Survival		Time of death or 2-years after last SBRT dose
6. Incidence of non-classic RILD, defined as grade 4 aspartate aminotransferase or alanine aminotransferase elevation, or an increase in CP score of $\geq 2$ within 1 week to 3 months after completing SBRT (Appendix A)		3 months after last SBRT dose

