#### 6.1.6 ADVERSE EVENT EVALUATION

Toxicities and adverse experiences will be assessed at each visit using the [CTCAE v5.0](#) and quantifying current Child-Pugh score to assess risk of RILD. Adverse events will be monitored from the time the participant signs the Consent Form up until 3 months following SBRT. Participants will be instructed to report all AEs during the study and will be assessed for the occurrence of AEs up until 3 months following radiation therapy. All AEs (serious and non-serious) must be recorded on the source documents and CRFs regardless of the assumption of a causal relationship with the study therapy.

For details on AE collection and reporting, refer to Section 8.6.

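### Every planned toxicity endpoint and analysis is hepatic, although the toxicity objective has no organ limit and all adverse events are collected

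*Combined protocol and SAP*

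**What the plan says.** The objective in Section 2.2 is broad: "Assess preliminary efficacy and toxicity in HCC patients with advanced cirrhosis following liver SBRT". Collection is equally broad. Section 6.1.6 states: "All AEs (serious and non-serious) must be recorded on the source documents and CRFs regardless of the assumption of a causal relationship". Sections 6.1.6 and 8.5 run that collection from consent to 3 months after SBRT, graded by CTCAE v5.0. Section 9.1 makes everyone evaluable for toxicity from the first fraction, again with no organ named.

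The endpoints are narrower. The synopsis has two for toxicity. Number 6 is "Incidence of non-classical radiation-induced liver disease (RILD), defined as grade 4 aspartate aminotransferase or alanine aminotransferase elevation", or a Child-Pugh rise of at least 2 points. Number 7 is "Incidence of liver toxicity per CTCAE v5.0 within 1 week to 3 months after completing SBRT". Section 3.2.2 carries only the first of these.

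Section 9.2.3 then lists the toxicity results: non-classic RILD, a Child-Pugh rise of at least 2 points, "and liver toxicity per CTCAE v5.0, will be estimated along with an exact CI using the safety analysis set". Section 9 has no table, rate or interval for any other adverse event.

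**The concern.** If the plan is followed exactly, the toxicity objective is answered for the liver only. The endpoint windows in the synopsis also open 1 week after SBRT is completed, so events during treatment and in the first week after it lie outside them.

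The protocol expects trouble elsewhere. Section 1.4.1 reports gallbladder perforation, upper gastrointestinal bleeding and thrombocytopenia at grade 4. Section 8.4.1 lists gastric ulceration and esophagitis. Table 3 sets dose limits for esophagus, stomach, duodenum, bowel, heart, chest wall and skin, yet no planned result would show how those organs fared.

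Section 9.3.1 gives the main goal as finding unforeseen problems before a larger trial. A liver-only result set mostly measures the problem already foreseen. What is at stake is how complete and how pre-specified the toxicity report will be. A summary of non-hepatic events that is chosen after the data are seen carries less weight than one fixed now.

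**Working it through.** **1. From objective to analysis.**

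| Step | Where | Organ scope |
|---|---|---|
| Objective | 2.2 | none stated |
| Collection and grading | 6.1.6, 6.8, 8.5 | all adverse events |
| Population | 9.1, safety analysis set | none stated |
| Endpoints | synopsis 6 and 7; 3.2.2 no. 6 | liver |
| Analyses | 9.2.3 | liver |

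The scope narrows at the endpoint step and stays narrow. The three analyses also overlap, because a Child-Pugh rise of at least 2 points is one arm of the RILD definition. Section 3.1 says toxicities associated with RILD will be evaluated, but gives no endpoint or method.

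**2. The protocol's own figure.** Section 1.4.1 states: "Only 11 of 146 patients (7.5%) were observed to have a Grade 4 toxicities". The breakdown follows: "These grade 4 AEs consisted of 1 gall bladder perforation, 4 cases of thrombocytopenia, 2 cases of hyperbilirubinemia, 2 cases of upper gastrointestinal bleeding". Encephalopathy makes up the remaining two. The sum is 1 + 4 + 2 + 2 + 2 = 11, and 11/146 = 7.5%. The figure reproduces.

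**3. Sorting the 11 against the protocol's liver definitions.** Appendix A scores albumin, ascites, INR, encephalopathy and bilirubin. The other arm of RILD is grade 4 AST or ALT.

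| Event | n | In Child-Pugh or AST/ALT? |
|---|---|---|
| Hyperbilirubinemia | 2 | yes |
| Encephalopathy | 2 | yes |
| Thrombocytopenia | 4 | no |
| Upper GI bleeding | 2 | no |
| Gallbladder perforation | 1 | no |

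Outside the definitions: 4 + 2 + 1 = 7, and 7/11 = 64%.

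**4. Sensitivity to classification.** The protocol has no list of terms for CTCAE liver toxicity, so other sortings are possible:

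- gallbladder perforation counted as hepatic: 6/11 (55%) remain outside;
- upper GI bleeding counted as hepatic: 5/11 (45%);
- thrombocytopenia counted as hepatic: 3/11 (27%);
- encephalopathy counted as non-hepatic: 9/11 (82%).

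**5. What an added endpoint could show at n = 15.** The exact (Clopper-Pearson) upper 95% limit for 0/15 is 1 − 0.025^(1/15) = 21.8%. The intervals are 0.2% to 31.9% for 1/15 and 1.7% to 40.5% for 2/15. These widths hold for any binary endpoint at this size. They show how little a count of zero would exclude, and do not measure the gap itself.

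**The case against.** The strongest reply is that non-hepatic toxicity will not go unseen. Every adverse event is recorded with severity, seriousness, expectedness and relationship (Section 8.5). The pause rule in Section 8.7 has no organ limit. The DSMC reviews toxicity every 6 months, and its material may include adverse events by category and deaths (Section 10.1). On this view only a summary method is missing. The facts are right and they rule out any claim that the data will be absent. But these provisions govern conduct and oversight, and none of them obliges a result in the final report. The pause rule also reaches a grade 4 event only if it is attributable and either unmanageable or unexpected, so a grade 3 event, or a manageable grade 4 bleed of an expected kind, would not trigger it.

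A second reply is that the liver focus is reasonable. Section 1.4.1 gives 31% for a Child-Pugh rise of at least 2 points within 6 months in patients with severely compromised liver function. It also cites 52% adverse events in a placebo arm to show how hard it is to separate treatment effects from cirrhosis. That justifies keeping the liver endpoints and reading an any-organ rate with care. It does not justify having no other result under an objective with no organ limit.

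A reader might infer two stronger points that the documents do not support:

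- **That the trial could declare SBRT safe while leaving out severe toxicity.** There is no safety success criterion and no formal hypothesis test, and nothing bars an ordinary adverse event table.
- **That most severe toxicity would be omitted.** The 7 of 11 covers grade 4 only, with no grade 3 breakdown. It comes from 146 patients with varying cirrhosis, of whom 51 were CP-B8 or higher, treated with SBRT or hypofractionated radiotherapy and followed for 6 months. Under some of the sortings above it is not a majority.

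**Conclusion.** The point holds as a mismatch between objective and analysis: toxicity of any organ is the stated aim and is collected, but only liver results are planned. This does not depend on how the 11 events are sorted, since gastric ulceration and esophagitis are not liver events under any reading.

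The size can be given only as an indication. In the cited series, 7 of 11 grade 4 events lie outside the protocol's defined liver measures, or 3 of 11 if thrombocytopenia is counted as hepatic. This rests on reading CTCAE liver toxicity as no wider than the Child-Pugh and AST/ALT terms, which the protocol neither confirms nor denies. The population, treatments and time window differ from this trial's, so the figure shows which kinds of event to plan for and is no forecast of their rate.

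The plan should be amended. The gap does not touch the primary endpoint or the sample size.

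**What to change.** Add one secondary endpoint to the synopsis, Section 3.2.2 and Section 9.2.3: the proportion of the safety analysis set with at least one CTCAE v5.0 adverse event of grade 3 or higher, in any organ system, from the first fraction to 3 months after the last fraction, with an exact 95% CI. The end of the window matches the end of adverse event collection, and the start takes in acute events that the liver endpoints miss.

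Accompany it with a table by organ system, grade and the causality categories of Section 8.2.5. If the table shows all grades, the grade 2 gastric ulceration foreseen in Section 8.4.1 also appears, which the grade 3 rate alone would leave out.

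Two related repairs belong in the same amendment. List the CTCAE terms that count as liver toxicity, so that classification is settled before the data are seen. Reconcile synopsis endpoint 7 with Section 3.2.2, where it is absent although Section 9.2.3 analyzes it. The liver endpoints otherwise stay.

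The cost is a paragraph, a term list and a table from data already collected, with no extra visits or participants. The downside is that the overall rate can be expected to exceed the liver-only rate and will include events due to underlying cirrhosis, so it should be read with the causality split.
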